8.5.4.2 Statistical Analysis

Statistical analyses will be generated using SAS (version 9.0 or higher) for the Mixed procedure. The natural logarithmic transformation of PK parameters as well as the rank-transformation of T_{max} will be used for all statistical inference. Subjects who do not have parameters for both DST-0509/Jadenu or DST-0509/Exjade treatments will not be included in the respective statistical bioequivalent analyses.

Exposure pharmacokinetic parameters (C_{max} , AUC) will be statistically analyzed using an Analysis of Variance (ANOVA) model. The fixed factors included in this model will be the treatment received, the period at which it was given as well as the sequence in which each treatment is received. A random factor will also be added for the patient effect (nested within sequence).

The 90% confidence interval for the exponential of the difference in LS means between Treatments will be computed. If there are sufficient data for both Jadenu and Exjade, both will serve as reference in the respective analysis, no pooling of data between the reference treatments (Jadenu, Exjade) will be performed.

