This current pilot study is a multicenter, open-label, two-period crossover design that evaluates the safety, tolerability, pharmacokinetics and preliminary evidence of iron chelating activity of DST-0509 as compared to Jadenu and Exjade in transfusion-dependent thalassemia patients with transfusional iron overload, requiring iron chelation therapy and demonstrating an inadequate response to Jadenu or Exjade for greater than 3 months duration. Up to 36 patients will be evaluated (18 in each treatment arm), however, the balanced randomization may enroll fewer patients based on recruitment status.

Rationale for the study design is detailed in [Section 3.2](#).

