3.1 Overall Study Design

This is a multi-center, open-label, two-period cross-over, patient-pilot study comparing DST-0509 to Exjade or Jadenu administered orally once daily (QD) for 28-days in each period, with a 7-day washout before study entry and between treatment periods (see Table 6-1). Patients will be randomized to one of two treatment sequences: DST-0509→Exjade/Jadenu or Exjade/Jadenu→DST-0509 (with subjects who were taking Exjade prior to study start receiving Exjade and those taking Jadenu at study start receiving Jadenu). This study is designed to assess the safety, tolerability, evidence of iron chelating activity, and PK profile of DST-0509 compared to Jadenu or Exjade in inadequately responding patients. Inadequate response to standard chelation therapy is defined from the medical literature [6,7].

Up to 36 patients will be randomized 1:1 into one of two treatment sequences (study arms), of which up to 100% may be on Jadenu or Exjade at study entry, or a mix of the two. The planned randomization will assign up to 18 patients in each of two sequences: Sequence A: DST-0509 crossed to Exjade or Jadenu; Sequence B: Jadenu or Exjade crossed to DST-0509. The comparator treatment will be the patient's current chelation treatment. At the end of the study, patients previously on Jadenu or Exjade will revert to receiving their pre-study medication and dose following a 7-day washout period. A sufficient number of patients will be enrolled so there will be no need to replace study drop-outs. Study duration is approximately 14 weeks for each patient. A Study Flow Diagram is presented after this Synopsis (see Figure 3-1).

Figure 3-1: Study Flow Diagram

Treatment A (28 days) = DST-0509
Treatment B (28 days) = Jadenu/Exjade¹

*Up to 36 patients are planned.

- Subjects taking Exjade prior to study start will receive Exjade (treatment B) in the assigned Period 1 or cross-over Period 2. Those patients taking Jadenu prior to study start will receive Jadenu (treatment B) in the assigned Period 1 or cross-over Period 2. Dosing will be at equivalent (mg for mg) doses of DST-0509 for Jadenu. If crossing over from Exjade to DST-0509, or vice versa, the dose will be scaled to 28 mg/40 mg (DST-0509/Exjade).
- For all patients entering the trial, a 7-day washout is required.

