5.3 Methods of Assigning Patients to Treatment Groups

Each clinical site will be assigned a unique 2-digit number. At each clinical site, a unique 3-digit screening number will be assigned to each patient after written IC is obtained. Patient screening numbers will be assigned sequentially at the site. Each patient will have a unique identifier that combines both the site and screening number. At Visit 3 (Day 1), a randomization number will be assigned centrally (by Accelovance, Inc. or by Interactive Voice Response System [IVRS], in accordance with the investigational product manufacturer) to each patient in a sequential manner as they become eligible for randomization. The randomization number will correspond to a predetermined treatment. Screening and randomization numbers must not be re-used once assigned, even if the patient does not take the investigational product.

Subjects who were taking Exjade prior to study start will receive Exjade at their prescribed dose during the study and those taking Jadenu at study start will receive Jadenu at their prescribed dose.

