8.4 Randomization

This study will investigate 2 treatment groups:

Group (Treatment)	Treatment Assignment
1 (A/B)	DST-0509 / Jadenu (Exjade)
2 (B/A)	Jadenu (Exjade) / DST-0509

A computer-generated randomization scheme will be used to obtain a balanced allocation to each treatment group.

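### Randomisation is not stratified by prior product although the PK comparisons are separate by product: a cheap improvement that protects the precision of the smaller reference group

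*Protocol*

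**What the plan says.** **Allocation.** Section 8.4 defines two groups, DST-0509 first or the reference first, and says: "A computer-generated randomization scheme will be used to obtain a balanced allocation to each treatment group". Section 3.1 gives the numbers: "The planned randomization will assign up to 18 patients in each of two sequences". Section 1.2 adds that "the balanced randomization may enroll fewer patients based on recruitment status". Under Section 5.3 a central process gives a randomisation number "to each patient in a sequential manner as they become eligible for randomization", each number tied to a treatment fixed in advance. None of Sections 3.1, 5.3, 6.3.1, 7.12 or 8.4 names a stratification factor.

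**Reference product.** This is whatever the patient took before the study. Section 5.3 says: "Subjects who were taking Exjade prior to study start will receive Exjade at their prescribed dose during the study", and likewise for Jadenu. Section 3.1 leaves the mix open, "of which up to 100% may be on Jadenu or Exjade at study entry, or a mix of the two".

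**PK analysis.** Section 8.5.4.2 fits C_max and AUC with treatment, period and sequence as fixed factors and patient within sequence as random. Only patients with parameters for both treatments enter. The rule for the two references is one sentence with a condition: "If there are sufficient data for both Jadenu and Exjade, both will serve as reference in the respective analysis", followed by "no pooling of data between the reference treatments (Jadenu, Exjade) will be performed". The Protocol gives no number of patients, in total or per sequence, at which data count as sufficient.

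**The concern.** The set of patients balanced by the randomisation (everyone) is not the set analysed (patients on one reference product). In a two-period crossover with a period effect, the treatment contrast is most precise when the two sequences are equal in size. It cannot be estimated at all if one sequence is empty. Balance over all 36 patients does not ensure balance within a small product subgroup.

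At stake is the precision of the exposure ratio against the less common product. PK is the only secondary objective (Section 2.2), and the synopsis hypothesises lower exposure on current therapy than on DST-0509 in many of these patients. A later analysis plan cannot repair the split, because sequence assignment is fixed at randomisation.

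**Working it through.** **The Protocol's own figure.** The only sample-size calculation (Section 8.1) concerns diarrhoea events at a 12% rate with N = 30.
- At least one event: 1 − 0.88^30 = 0.978 (stated 98%).
- At least two: 1 − 0.88^30 − 30 × 0.12 × 0.88^29 = 0.890 (stated 89%).

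Both reproduce. No figure is given for PK precision or for the size of either reference group, so the rest rests on a stated assumption.

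**Inputs.** N = 36 with 18 per sequence (Section 3.1); one list balanced overall (Sections 5.3 and 8.4). Let m be the number of patients on the less common product. The Protocol does not give m, so a range is shown.

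**Chance of a poor split.** The number of the m patients in the first sequence is hypergeometric: P(a) = C(18, a) × C(18, m − a) / C(36, m).
- m = 4, one sequence empty: 2 × 3060 / 58905 = 10.4%. Exactly 3:1: 2 × 816 × 18 / 58905 = 49.9%. So 3:1 or worse is 60.3%.
- m = 6, one sequence empty: 2 × 18564 / 1947792 = 1.9%. Exactly 5:1: 2 × 8568 × 18 / 1947792 = 15.8%. So 5:1 or worse is 17.7%.

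| m | One sequence empty | At most one patient in a sequence |
|---|---|---|
| 4 | 10.4% | 60.3% |
| 5 | 4.5% | 33.8% |
| 6 | 1.9% | 17.7% |
| 8 | 0.3% | 4.1% |
| 10 | 0.03% | 0.7% |

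At m = 8, a split of 6:2 or worse has probability 22.8%. With N = 30 or 24 the values are slightly lower (m = 4, empty: 10.0% and 9.3%).

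**Cost of a poor split.** The variance of the treatment contrast is proportional to 1/a + 1/b. Relative to an even split this is m² / (4ab), and the standard error grows by its square root.
- 3:1 gives 16/12 = 1.33, standard error 15% larger.
- 5:1 gives 36/20 = 1.80, standard error 34% larger.
- 6:2 gives 64/48 = 1.33, standard error 15% larger.

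**Empty sequence.** With four patients all in one sequence, the matrix of four patient columns plus period and treatment has rank 5 for 6 columns. Treatment is aliased with period. At 3:1 the rank is the full 6.

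**The larger group.** A 4:0 split in the minority leaves 14:18 in the majority: 32² / (4 × 14 × 18) = 1.016. A 5:1 split leaves 13:17: 30² / (4 × 13 × 17) = 1.018.

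**Interval width.** The 90% interval multiplies and divides the ratio by exp{t(0.95, m − 2) × s × √[½(1/a + 1/b)]}, with s = √ln(1 + CV²). The within-patient CV is an assumption. At m = 6 and CV 30% (s = 0.294, t = 2.132) the factor is 1.44 for 3:3 and 1.62 for 5:1. Over CV 20% to 40% it runs from 1.28 to 1.61 for 3:3 and from 1.39 to 1.89 for 5:1.

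**The case against.** The strongest reply is that the separate comparisons are conditional. A group of four patients in one sequence is exactly what the condition on sufficient data would most naturally remove. That is fair, and the no-pooling clause should not be read without it. But the condition has no threshold and no minimum per sequence. It permits a comparison to be dropped; it does not prevent the imbalance.

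A reader might infer that the PK comparison as a whole is at risk, that the estimates would be biased, or that non-estimability is a general hazard. The documents do not support any of these.
- The model contains period, so while both sequences are represented an uneven split costs precision only.
- The larger reference group loses under 2% in variance in the cases shown.
- An empty sequence is a material risk only at about five patients or fewer. If everyone takes one product, which Section 3.1 allows, the issue disappears.

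It also stands that PK is secondary in a pilot whose size rests on adverse-event detection, and that Section 8.5.4.2 sets no acceptance limits, so a wider interval changes no stated decision. Small numbers limit a minority group more than imbalance does: even at 3:3 the factor is 1.44. Finally, Sections 5.3 and 8.4 contain no false statement, and block details are often left to a randomisation specification. These points lower the severity. They do not remove the mismatch between the balance provided and the analysis planned.

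**Conclusion.** The point holds as a low-severity improvement, not as an error in the Protocol. If both products are enrolled and the less common one has about six patients or fewer, its sequence split has a substantial chance of being poor. From about eight patients the typical bad case is 6:2, with a standard error about 15% larger.

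This rests on an assumed product mix, on exact 18/18 balance overall, and on all randomised patients being analysed. If patients in the subgroup were instead assigned independently at one half each, the chance of an empty sequence at m = 4 would be 2 × 0.5^4 = 12.5%, so the overall-balance assumption is not what drives the result. Drop-outs are not replaced (Section 4), so the analysed split may be worse than the randomised one.

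**What to change.** In Section 8.4, stratify the central randomisation by prior product (Jadenu or Exjade), which is known before Day 1. Use small permuted blocks whose sizes vary and are concealed from the sites, since in an open-label study short blocks of known size make later assignments easier to guess.

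With blocks no larger than 4, the two sequences within a product differ by at most 2 patients at randomisation. An empty sequence is then impossible for three or more patients, and the worst split at m = 6 is 4:2 (variance ×1.125) instead of 5:1 or 6:0. It would also help to state in Section 8.5.4.2 the minimum number of evaluable patients per sequence at which data count as sufficient.

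The cost is two lists instead of one, and each sequence may end one or two patients away from half of the total. Stratifying does not cure the small size of a minority group, nor drift from drop-outs that are not replaced.

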9 ADVERSE EVENT MONITORING

9.1 Definition

An AE is defined as any untoward medical occurrence in a patient or clinical investigation following the patient's first dose of investigational product that does not necessarily have a causal relationship with this treatment. An AE can be any unfavorable or unintended sign (including an abnormal finding), symptom, or disease temporally associated with the use of a medicinal (investigational) product, whether or not related to the medicinal (investigational) product.

This includes any occurrence that is new in onset or aggravated in severity or frequency from the baseline condition (including the physical examination), or abnormal results of diagnostic procedures (including laboratory test abnormalities).

Events should be considered AEs if they:

- result in discontinuation from the study,
- require treatment or any other therapeutic intervention,
- require further diagnostic evaluation (excluding a repetition of the same procedure to confirm the abnormality),
- are associated with clinical signs or symptoms judged by the Investigator to have a significant clinical impact.

Clinically Significant Laboratory Changes: It is the Investigator's responsibility to review the results of all laboratory tests as they become available. For each abnormal result, the Investigator needs to ascertain whether the abnormality presents a clinically significant change from baseline. If the change is due to the expected course of the patient's underlying disease (e.g., elevated cholesterol in a study of dyslipidemia), it is not considered an adverse event unless the abnormality is more severe than expected. A laboratory test may be confirmed by repeat testing or other diagnostic tests before being considered an adverse event. If the laboratory abnormality is a significant change from baseline for the patient, then it should be considered an adverse event.

An Adverse Event is not:

- A surgical procedure
- A situation where an untoward event did not occur, (e.g. a social hospitalization)
- The disease being studied, unless progression is more severe than anticipated
- Lack of efficacy
- Baseline conditions that have not worsened in severity or frequency
- Clinically significant abnormal laboratory findings or test results related to the disease being studied (unless more severe than expected)

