9.2 Procedures

An untoward event that occurs after screening and before the first dose of investigational product will be recorded as an update to the medical history.

Some events may make the patient ineligible for randomization. Unanticipated events should be reported to the IRB, according to its requirements.

Patients will be questioned at every visit after the first dose until Visit 11 or ET regarding the occurrence and nature of any AEs. All AEs will be reported, whether or not they are deemed to be related to investigational product.

A description of the event or diagnosis including dates, severity, relationship to the investigational product, action taken with the study drug and outcome, and whether or not the event was also serious, must be reported on the AE CRF for each adverse event recorded in the patient's chart.

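### Section 9.1 gives conflicting rules on whether a clinically significant laboratory change put down to the disease is an adverse event, and Section 6.6 conflicts with it on withdrawals

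*Protocol*

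**What the plan says.** Protocol Section 9.1 starts from a definition that ignores cause: a sign, symptom or disease "temporally associated with the use of a medicinal (investigational) product, whether or not related to the medicinal (investigational) product". Under the lead-in "Events should be considered AEs if they" it lists four triggers, also free of cause. They include leading to discontinuation and to "require treatment or any other therapeutic intervention".

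The laboratory paragraph of 9.1 then says two things. Of a change due to the expected course of the underlying disease it says "it is not considered an adverse event unless the abnormality is more severe than expected". It closes with: "If the laboratory abnormality is a significant change from baseline for the patient, then it should be considered an adverse event".

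The list of what an AE is not adds two exclusions: "The disease being studied, unless progression is more severe than anticipated" and "Clinically significant abnormal laboratory findings or test results related to the disease being studied (unless more severe than expected".

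Section 9.2 says "All AEs will be reported, whether or not they are deemed to be related to investigational product". Section 9.4 provides a related / not related field for each AE. Section 9.8 defines a serious adverse event (SAE) as an AE with one of the listed outcomes. Section 6.6 offers, as a reason for withdrawal, a laboratory abnormality that falls short of being an AE.

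**The concern.** The exclusions in 9.1 make the investigator decide cause before an AE record exists. If the change is put down to thalassemia or iron overload and judged no worse than expected, no AE is entered and the relationship field of 9.4 is never reached.

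This matters here for three reasons. Safety and tolerability are the primary endpoints (Section 8.1). The study is open-label (Section 5.6), so the judgment is made with treatment known. And the drug's known toxicities resemble the disease. The appended Exjade label reports neutropenia, thrombocytopenia and worsening anemia, with a risk that existing hematologic disorders may raise (label 5.4, 6.2), as well as ALT elevations and hepatic injury (label 5.2, 6.1). Protocol Section 1.2 notes hepatic failure, especially with existing cirrhosis.

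A statistical analysis plan cannot repair this, because it cannot recover events that sites never entered.

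**Working it through.** The point concerns wording, so the check applies each rule to the same case.

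**Case 1: ALT.** Take a patient at 2 x ULN at baseline, a level Section 4.2 allows (limit 2.5 x ULN), who reaches 6 x ULN by Day 28. The values are illustrative. The investigator finds the change clinically significant and thinks iron overload explains it.

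| Rule in 9.1 | Is it an AE? |
|---|---|
| General definition, regardless of relationship | Yes |
| Significant change from baseline | Yes |
| Expected course of the disease | No, unless worse than expected |
| Laboratory finding related to the disease | No, unless worse than expected |
| Four triggers | Yes, if one applies |

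The section does not rank these rules and gives no threshold or reference for expected. Its only example is cholesterol in dyslipidemia.

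**Case 2: hemoglobin.** A fall from 9 to 7 g/dL (entry is allowed from 8 g/dL) gives the same split. It also meets the separate exclusion for the disease itself.

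**Case 3: discontinuation.** Under 9.1, an event that results in discontinuation is an AE. Under 6.6, a patient can be withdrawn for a laboratory abnormality that is not one. Section 8.5.3 counts patients with an AE associated with study discontinuation, so the same withdrawal is inside or outside that count depending on the section followed.

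**Downstream.** Because 9.8 builds the SAE on the AE, a finding denied AE status cannot be an SAE.

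**Do the laboratory summaries compensate?** Section 8.5.3 plans mean, median, SD, minimum and maximum by visit, and low/normal/high shifts.
- Shift table: ALT from 2 to 6 x ULN is high-to-high. Hemoglobin from 9 to 7 g/dL is low-to-low, assuming a lower limit of normal above 9. Neither shows as a shift.
- Mean: with 36 patients, the ALT case moves the mean by (6 - 2)/36 = 0.11 x ULN. The hemoglobin case moves it by (9 - 7)/36 = 0.06 g/dL.
- The minimum and maximum show the most extreme value at a visit, and Section 8.5 plans listings. The values are therefore not lost, but they do not enter an AE or SAE count.

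**The plan's own figures.** Section 8.1 gives 98% for at least one diarrhea AE and 89% for at least two, at a 12% rate and N = 30.
- At least one: 1 - 0.88^30 = 0.978.
- At least two: 1 - 0.88^30 - 30 x 0.12 x 0.88^29 = 0.890.

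Both reproduce. They rest on a symptom, not on a laboratory value, and are untouched by this point.

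**The case against.** The strongest reply is that 9.1 states a rule and an exception, not a contradiction: significant changes are AEs, except those in the expected course of disease, and a change worse than expected comes back in. With the screening limits of Section 4.2 and 28-day periods, a marked new abnormality would often meet that test. Discontinuation, treatment or further work-up also makes an event an AE whatever its cause. The reading is possible, and it narrows the problem. But the sentence on significant change comes after the carve-out and carries no condition on cause, the exclusion list covers findings already judged clinically significant, and expected has no reference. Two sites could apply the text differently and both be following it. The reply also leaves the conflict with 6.6 in place.

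A reader might infer more than the documents support:
- *That all disease-attributed changes stay out.* The exception and the four triggers prevent that. An SAE would usually meet a trigger, so its loss depends on a site letting the exclusion override the triggers.
- *That mild diarrhea could escape as well.* It could not. The four triggers are sufficient, not necessary; the main definition covers any symptom; Section 9.3 grades mild events; and diaries capture gastrointestinal events (7.14, 8.5.3).
- *That cytopenia suspension would fail.* That rule in 8.5.3 rests on the counts themselves, not on AE status.
- *That the label's ALT rates size the effect* (ALT above 5 x ULN at two consecutive visits: 17/296 = 5.7% on deferasirox, 5/290 = 1.7% on deferoxamine). Deferoxamine is an active chelator, not an untreated control, and treatment lasted about a year. Applying an assumed share attributed to disease would only return that assumption.
- *That the bias favors one treatment.* Each patient receives both treatments with the same disease. A difference is possible because treatment is known, but it is not shown.

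**Conclusion.** The concern holds in limited form. Section 9.1 conflicts with itself on clinically significant laboratory changes attributed to the disease, and with 6.6 on laboratory withdrawals. Some hepatic, blood-count and hemoglobin changes can therefore be missing from the AE, SAE and AE-discontinuation counts of an open-label trial whose primary endpoints are safety and tolerability. They would still be in the laboratory data, which compensate only in part.

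The size and direction cannot be estimated, because the documents do not say how often investigators would attribute such changes to disease or what they would regard as expected. The conclusion rests on the wording and on the overlap between labelled toxicities and the disease, not on a rate. It should be corrected because it concerns the primary safety record and takes only a text change.

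**What to change.** Reconcile 9.1 internally and with 6.6:

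1. For the labelled tests that overlap with the disease (ALT/AST, bilirubin, platelets, neutrophils, hemoglobin), record every clinically significant worsening from baseline as an AE whatever its presumed cause.
2. Enter attribution only in the relationship field of 9.4.
3. State that none of the three exclusions (expected course, the disease itself, findings related to the disease) applies to these tests. They may stay for iron markers such as ferritin.
4. Count any withdrawal for a laboratory abnormality as an AE-related discontinuation, and change the 6.6 category to match.

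This concerns recording only and changes no rule on dosing or stopping. It costs a protocol wording change, matching CRF guidance and somewhat more AE entries, with no new tests or visits.
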